Along with decrease beta-cell function, youth with type 2 diabetes become resistance to pharmacological mono-therapy (metformin or rosiglitazone) and lifestyle intervention such as change in diet and physical activity. Due to these limiting factors, once a pre-diabetic child or adolescent develops type 2 diabetes, it is considered irreversible (Zeitler et al, 2012.) Given this, the focus is on early prevention of on-set prediabetes or type 2 diabetes among the obese youth population. Early lifestyle prevention and intervention programs consist of changing diet, physical activity and lifestyle habits (i.e taking the stairs instead of the elevator) through education. A number research study-programs have shown promising results in regards to diabetes prevention such as: 42% reduction of whole body insulin sensitivity, a two- fold greater change in body fat than body weight, increase lean body mass, and normalized fasting, two-hour plasma blood glucose levels, and decrease LDL cholesterol levels (Shaw, 2009, Wadden, 2012.) In addition to the physical and metabolic impact of obesity, research supports the relationship between obesity, mental health, and health behaviors. Generally, overweight and obese youth have increased mental health concerns compared to their normal weight peers (Sinha, 2002.) Specifically, obesity has been linked to presence of depression, anxiety, attention deficit hyperactivity disorder, and conduct disorder among children (Halfon, 2013, Puder, 2010.) Difficulty coping with stress and decreased selfesteem are also associated with obesity (BeLue, 2009.) Studies have also shown that individuals, adults and youth, with type 2 diabetes have decreased cognitive functioning including mental processing speed, flexibility, memory, and learning (Puder, 2010.) Physical activity participation has been linked with improved academic performance, mental health, and cognitive function (Hillman, 2008.) Despite these findings, the best treatment or weight management for childhood obesity is still uncertain. A few studies have examined the cumulative impact of improving physical activity, fitness, nutrition, and overall health behaviors in children.

The specific aims of this research project are to:

- 1) Examine the change of health status of youth participants over time as a result of the 12-month (16 weekly, 3 biweekly, and 6-monthly session) ISC intervention through the evaluation of metabolic, physical fitness, and health habit parameters

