- 2) Examine the change of health status of parent participants over time as a result of the 12-month (16 weekly, 3 biweekly, and 6-monthly session) DPP adult sessions through the evaluation of metabolic, physical fitness, and health habit parameters.

3. Study/Project Population,

Potential subjects and their parents will be informed of the study through flyers, community events, and physician referrals. Flyers will be distributed/posted at all YMCA sites and physician offices and clinics, throughout Memphis.

Inclusion criteria for youth participants will include:

- 1) Between 7-15 years-old
- 2) Hemoglobin A1C 5.7-6.4% or BMI \geq 85th percentile, parent **or** grandparent with pre/type II Diabetes
- 3) Able to participate in physical activity
- 4) Parent or caregiver participation

Exclusion criteria for youth participants will include:

- 1) Pregnant females
- 2) Those with mental health illness (e.g. depression, ADHD, etc.)
- 3) Medications that would interfere with testing results (e.g. metformin, insulin)

Inclusion criteria for parent participants will include:

- 1) ≥18 years-old
- 2) At least one child enrolled in ISC
- 3) Able to participate in physical activity

Exclusion criteria for parent participants will include:

- 1) Those with mental health illness (e.g. depression, ADHD, etc.)
- 2) Medications that would interfere with testing results (e.g. metformin, insulin).

Inclusion and exclusion criteria will be assessed via parent and child self/physician referral form. The UTHSC/LBCH subcommittee will approve all procedures for the Use and Protection of Human Subjects. ISC and control group participants will be assigned on a fist come first serve basis.

Consenting and Questionnaires:

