This project will employ a quasi-experimental non-control group design with an intervention group (ISC). The intervention group will receive the ISC curriculum, which promotes healthier physical activity, nutrition, sleep, and stress coping practices. The intervention phase will consist of 12-months: registration, six evaluation sessions (2-3 hours per evaluation: Week 1, 8, and 16, 6-month, 9-month, and 12-month), and 16-weekly, 3-bi weekly, 6-monthly educational and physical activity sessions (1.5 hours per session: 45-minutes of health education and 45-minutes of physical activity). Youth between the ages of 7-15 throughout Shelby County will be recruited to participate in this study. Recruitment, data collection, and program implementation will be accomplished through a community-academic partnership between UTHSC/LBCH and the YMCA. Upon obtaining parental consent and child assent, all data collection will occur at the Gaisman Community Center site under the supervision of UTHSC/LBCH staff.

Incentives

Pre, post, and follow-up evaluations: \$50 gift card for participant

Programs sessions: attendance raffle: participants will be provided with a raffle ticket for attending sessions and will be able to select a n item for a prize box (water bottles, t-shirts, jump ropes, hand sanitizer, myPlates, etc.)

5. Study/Project Procedures

Research and Program Setting. The YMCA of Memphis & the Mid-South's mission is to put faith-based principles into practice through programs that build healthy spirit, mind, and body while strengthening communities. The YMCA is the largest provider of before/after school services serving children in the Shelby County, Tennessee and Desoto County, Mississippi School Districts, and selected schools in the

Marion School District in Marion, Arkansas; thus being a major provider of after school care in the Mid-South.

All data collection and program activities with youth and their families will be located at the Gaisman Community Center. All tests and program activities will be under the supervision of UTHSC/LBCH and YMCA staff by trained researchers and staff.

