Physical Activity. An accelerometer (Computer Science and Applications, Inc., Shalimar, FL), will be used to assess physical activity (Epistein, 1996; Sallis 1990) The child will be asked to wear the accelerometer for 7-days. To ensure good reliability of devices use the children and parents will be taught how to use the accelerometers during a home visit and reminded of wear via a phone call. The PI and a research team member will schedule and conduct the home visits (pick-up and drop-off) with the parent and child. The home visits will provide an opportunity for detailed instruction and demonstration of device use as well as provide accountability of the device. The home visits will take approximately 30 minutes to complete. Metabolic Parameters. The metabolic parameters will take approximately 30 minutes to complete and will be administered by a trained health specialist under supervision of a medical director. The Inbody-570 multi-frequency bioimpedance analyzer (Biospace, Beverly Hills, CA), will be used to assess body composition (Inbody 570, 2006.) Information recorded will include: body weight, percent body fat, and BMI. Height (centimeters) will be measured using a Weigh Beam Eye-Level physicians' scale in cm (DETECTO, Webb City, MO, USA). A portable anthropometer (Lafayette Instrument Company, Lafayette, IN) will be used to measure sagittal abdominal height (SAH), as a predictor of visceral abdominal fat(Sampaio, 2007.) A Gulick spring loaded measuring tape (Dunlee, Aurora, IL) will be used to indicate central obesity (Center of Disease and Control, 2012.) Systolic and diastolic blood pressure (SBP and DBP respectively) will be taken using a manual sphygmomanometer (blood pressure cuff) with a child's cuff placed over the brachial artery (Tycos Instruments Inc., Arden, NC) using standard procedures (Kirkenale, 1967.) Resting heart rate will be measured manually after five minutes of seated rest through palpating radial pulse over 60 seconds and will be recorded as beats per minute (American Heart Association, 1996.) A1C will be assessed from a fingerstick capillary whole-blood sample using an A1CNow device (John & Edwards, 1994) (PTS Diagnostics, Indianapolis, IN). Lipid profile will measure total cholesterol, triglycerides, and LDL and HDL levels using Cholestech LDX (Alere, San Diego, CA.) Physical Fitness. The physical fitness assessments will take approximately 1 hour to complete and will be administered by a trained research staff under supervision of an exercise physiologist. The National Institute of Health's (NIH) two-minute walk test will be used to measure aerobic endurance (NIH, 2012). A Jamar plus handgrip dynamometer (Sammons Preston, Bolingbrook, IL) will used to measure grip

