Physical fitness (cardiorespiratory, muscular strength and endurance, and motor skills): The fitness battery will include the NIH two-minute walk test (aerobic fitness), handgrip strength, wall-sit (lower body strength), push-ups (upper body strength), curl-ups (abdominal strength), unilateral balance, 50-foot shuttle run (agility), and sit-and-reach box (lower body flexibility).

Metabolic Parameters (total and central adiposity, blood pressure, physiological stress): These measures include the Inbody-570 multi-frequency bioimpedance analyzer (body composition), Weigh Beam Eye-Level physicians' scale (height), anthropometer (sagittal abdominal height), Gulick spring loaded measuring tape (central obesity), sphygmomanometer (systolic and diastolic blood pressure), radial pulse (resting heart rate), A1C (blood glucose levels) and lipid profile (total cholesterol, triglycerides, and LDL and HDL levels.)

Health Habits (physical activity, nutrition, self-efficacy): Self-report measures will include knowledge, physical activity, sedentary habits, nutrition, and stress management.

Mediators: A parent- and child-report healthy habits questionnaire (adapted from previous research) will be used to assess demographics (i.e. age, race/ethnicity, SES, home environment), child's academic status, family health history, weight perception, and frequency and range of typically consumed foods, exercise, sleep, and healthy-lifestyle behaviors.

Analysis: We will use mixed repeated measures ANOVA model time as the outcome and physical fitness, metabolic parameters, and health habits as our predictor variables. We will also include possible covariates (race, ethnicity, SES, age, and BMI-Z) in the models.

22.0 (1075) Background & Current Status of Work in the Field

22.1 * Provide a discussion of the background and current status of work in the field.

* This section must provide a justification and rationale for conducting the study/project.

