32.:	* Does this study include creating a specimen repository or a data registry/repository? A repository is established when there is a plan to make stored data and/or specimens available for later use in other research studies.	being
	Yes No	
33.	0 (1734) Use of Other Data/Specimen Repositories	
33.:	1 * Will this project/study involve using data/specimens from other repositories?	
	Yes No	
34.	0 (1735) Discontinuation, Endpoints, Analyses	
34.:	1 * Describe the criteria for discontinuation of treatment and withdrawal of the subject from the study/project.	
N/A	A	
34.2	2 * Describe the endpoints or outcomes being assessed in the study/project, such as efficacy and safety endpoints.	
Ch Ba: Ch Ba: (Ti	tcome Measures: ange Over Time: Intervention seline (Time: 0) by changes over time (mid-intervention (Time: 1), and post-intervention (Time: 2)) ange Over Time: Maintenance seline (Time: 0) by changes over time (3-months out (Time: 3), 6 months out (Time: 4), 9 months out me: 5), 12 months out (Time: 6) st-intervention (Time: 2) by changes over time (3-months out (Time: 3), 6 months out (Time: 4), 9 onths out (Time: 5), 12 months out (Time: 6))	
34 1	3 * Describe the statistical analysis that will be used.	
J-7	Describe the statistical analysis that will be used.	
Phyto how physical ph	mary Predictors: ysical Activity: An accelerometer (Computer Science and Applications, Inc., Shalimar, FL), will be used assess physical activity. To ensure good reliability of devices used, children and parents will be taught w to use the accelerometers and reminded to wear them via a phone call. Self-report measures of ysical activity and sedentary habits will also be obtained. ysical fitness (cardiorespiratory, muscular strength and endurance, and motor skills): The fitness ttery will include the American Thoracic Society six-minute Walk Endurance Test (aerobic fitness) while onitoring pulse oximeter (blood oxygen), Jamar plus handgrip dynamometer (grip strength), MicroFET-2 indheld dynamometer (maximal isometric strength), sit-and-reach box (lower body flexibility), 30-foot uttle run (agility), and Bruininks-Oseretsky Test of Motor Proficiency (fine and gross motor control	

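### Youth blood pressure and resting heart rate are judged by within-child change to 12 months with no control group and no growth-referenced scale, so on raw scales growth is mixed with programme effect at the later visits

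*Combined protocol and SAP*

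**What the plan says.** - **Aim.** Section 21.1 item 2, Aim 1: "Examine the change of health status of youth participants over time as a result of the 12-month" programme. Section 21.1 item 3 sets the youth age range at 7-15.
- **Design.** Section 21.1 item 4: "This project will employ a quasi-experimental non-control group design with an intervention group (ISC"). Evaluations fall at "Week 1, 8, and 16, 6-month, 9-month, and 12-month". Section 26.1 gives one year of participation per subject.
- **Contrasts.** Every contrast in 34.2 is within participant, from Time 0 or from Time 2. The maintenance lines run over "changes over time (3-months out (Time: 3), 6 months out (Time: 4), 9 months out me: 5), 12 months out (Time: 6"). No between-group contrast is listed.
- **Measures.** Section 21.1 item 5: "Systolic and diastolic blood pressure (SBP and DBP respectively) will be taken using a manual sphygmomanometer". Resting heart rate "will be recorded as beats per minute". Neither there, nor in item 6, 34.2 or 34.3, is a percentile, z-score or other age or height reference given for either measure.
- **Covariates.** Section 21.1 item 6 lists "possible covariates (race, ethnicity, SES, age, and BMI-Z) in the models". Section 34.3 keeps age, drops BMI-Z and adds grade. Neither says whether age is taken at entry or at each visit.
- **Traces of a comparator.** Section 21.1 item 3 says "ISC and control group participants will be assigned on a fist come first serve basis", and Aim 3 in section 22.1 refers to an educational control group. No control procedures and no group term in the model are described.

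**The concern.** Within one child, age and time since enrolment advance together. A measure that drifts with growth will change over a year whether or not the programme works, and a design without concurrent controls cannot separate the two on a raw scale. My assumption, which the documents do not state, is that between 7 and 15 blood pressure tends to rise with growth and resting heart rate tends to fall with age.

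The two distortions would then run in opposite directions. A child whose blood pressure improves relative to peers could look unchanged at 12 months, while part of an ordinary age-related fall in heart rate could be credited to the programme. Aim 1 makes exactly that attribution. BMI-Z shows that the plan knows of growth-referenced quantities, but it enters only as a covariate and does not rescale blood pressure or heart rate.

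**Working it through.** The plan states no effect size, SD, alpha, power or drift, so there is no figure of its own to reproduce.

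**From the documents:** youth aged 7-15; last evaluation at 12 months; accrual of 100, which covers youth, parents, screen failures and withdrawals (24.1), with no youth/parent split.

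**Assumed:** 30 or 50 youth with complete pairs; SD of change 8 or 10; two-sided alpha 0.05; true systolic effect -3 mmHg; growth drift +1 to +2 mmHg per year; heart rate drift -0.5 to -2 beats/min per year.

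**Step 1: mean change.** Observed change = programme effect + drift per year x years elapsed.

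- Week 16: drift = (1 to 2) x 16/52 = 0.3 to 0.6 mmHg.
- Month 12: -3 + 1 = -2, and -3 + 2 = -1. So 1/3 = 33% to 2/3 = 67% of the fall is hidden.

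**Step 2: significance at 12 months.** Paired t-test, noncentral t with n - 1 degrees of freedom and noncentrality = mean change / (SD/√n). For example, n = 50 and SD 8 give a standard error of 8/√50 = 1.13. The noncentrality is -2.65 with no drift and -0.88 with 2 mmHg drift.

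Power to show a true 3 mmHg systolic fall:

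| n | SD | No drift | +1/year | +2/year |
|---|---|---|---|---|
| 50 | 8 | 0.739 | 0.410 | 0.137 |
| 50 | 10 | 0.548 | 0.283 | 0.103 |
| 30 | 8 | 0.510 | 0.262 | 0.097 |
| 30 | 10 | 0.355 | 0.184 | 0.076 |

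Chance of a significant heart rate fall with no programme effect (nominal 0.025):

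| n | SD | -0.5/year | -1/year | -2/year |
|---|---|---|---|---|
| 50 | 8 | 0.063 | 0.137 | 0.410 |
| 50 | 10 | 0.053 | 0.103 | 0.283 |
| 30 | 8 | 0.052 | 0.097 | 0.262 |
| 30 | 10 | 0.045 | 0.076 | 0.184 |

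**Step 3: does the age covariate remove the drift?** The plan words time as the outcome, so its model cannot be run literally. The check used a random-intercept model with the measure as outcome, time as a factor and the six scheduled visits, with 2,000 trials per setting. Further assumptions were entry ages uniform from 7 to 16 and a between-child SD of 8. Results for systolic pressure, 50 youth, 12 months, drift 1-2 mmHg/year, SD 8-10:

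- Age at entry: power 0.105-0.436, essentially the unadjusted result.
- Age updated at each visit, between-child age slope equal to within-child growth: power 0.514-0.682, most of the loss recovered.
- Age updated, slope half of growth: power 0.275-0.524.
- Age updated, slope 1.5 times growth: over-correction, with false significant falls in 0.048-0.126 of trials with no effect.

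**Step 4: longer horizon, as a sensitivity only.** If the months out are counted from week 16, the last point is week 16 + 52 = 68. Drift is then 1 x 68/52 = 1.3 to 2 x 68/52 = 2.6 mmHg, and a 3 mmHg fall shows as 1.7 to 0.4 mmHg. False heart rate falls occur in 5-62% of trials.

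Diastolic pressure was not quantified.

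**The case against.** **The mechanism and its size come from outside the documents.** This stands. The direction of drift, its rate, the SDs, the 3 mmHg effect and the number of youth are all assumed, and the low end of the heart rate range is close to nominal. What the documents do establish is the structure: growing children, own-baseline contrasts, no concurrent control and no growth reference.

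**The raw scale is inferred from silence.** This also stands. A reader might infer that the plan commits to analysing mmHg and beats per minute. It does not: beats per minute is a recording unit, no unit is given for blood pressure, and BMI is recorded while BMI-Z is modelled. The plan leaves the analysis scale open, and nothing in it points to a growth-referenced one.

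**Age is in the model.** A reader might infer that the covariate cannot help at all. That is too strong: visit-updated age with a matching slope recovers most of the power. But the plan does not specify that reading, and the correction fails or overshoots when the slopes differ.

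**There may be a control group.** A comparator of similar age would largely cancel the drift. Besides the two mentions given above, the site table in section 23 lists an undefined second programme (WSC), and item 3 speaks of assignment. Against this, item 4 states a non-control design and 34.2 contains only within-participant contrasts.

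**Other items share the problem.** Raw fitness measures may also change with growth, and rescaling two variables does not repair uncontrolled attribution. Both are true. They limit the reach of the fix but do not argue against it.

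**Conclusion.** The point holds. As written, the plan cannot distinguish growth from programme effect for youth blood pressure and resting heart rate at months 6, 9 and 12 if raw values are compared. Under the stated assumptions, 33-67% of a true 3 mmHg systolic fall is hidden at 12 months. Power drops from 55-74% to 10-41% with 50 youth, and from 36-51% to 8-26% with 30. False significant heart rate falls occur in about 5-41% of trials. At week 16 the drift is minor.

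Two stronger conclusions are not supported:

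- A reader might infer that the blood pressure result will be biased against the programme overall. Regression to the mean and cuff habituation can pull readings down, so the net direction is uncertain.
- A reader might take the 68-week figures as the main case. The visit schedule, the final evaluation visit and the one-year participation in 26.1 all point to 12 months.

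This is a change the sponsor should make, with medium confidence: the gap is documented, its size is not, and the remedy is cheap.

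**What to change.** In 34.2 and 34.3:

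1. Analyse youth systolic and diastolic pressure as change in age-, sex- and height-standardised z-scores from one paediatric reference named in the plan. Recompute them from age and height at each visit, and keep mmHg as descriptive.
2. For youth heart rate, use age-referenced z-scores from a named source, or report the change descriptively and do not attribute it to the programme.
3. Analyse parents separately, in raw units.
4. State whether the age covariate is entry age or visit age, and whether the months out are counted from baseline or from week 16.
5. Define the control group in 21.1 item 3 and 22.1 Aim 3, or delete it.

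**Cost.** Derivation code and wording. Height is already among the evaluation measures and age is already asked. Sex appears only in the questionnaire list in 34.3, not in the lists in 21.1, so confirm that it is recorded.

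**Downsides.** Z-scores are less familiar than mmHg. They remove drift only if the reference fits, and a cohort selected on A1C, BMI or family history may not match it. Regression to the mean, cuff habituation and the other biases of a single-arm design remain, as does growth in the raw fitness measures.

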- **35.2** * Please utilize the following table to describe the risks associated with participation in this research. Include physical, psychological, social, legal, and any other risks.

Column 1: Type in the name of the procedure.

Columns 2-6: Identify the risks and their rate of occurrence in the appropriate column.

NOTE: If the study/project literature or the sponsor cannot provide the rate of occurrence of a risk, make an educated guess as to its rate of occurrence and type the word "Estimated:" before typing in the description of the risk.

Procedure	Very Common: occurs >50 times out of every 100	Common: occurs 21-50 times out of every 100	Occasional: occurs 6-20 times out of every 100	Rare: occurs 1- 5 times out of every 100	Very Rare: occurs less than 1 time out of every 100
					Estimated: Risks are expected to be minimal. There is a small risk that during the physical fitness measures and sessions, a student may fall, but will be no greater risk than that seen during normal

	Physical Activity	None	None	None	None	physical activity and outdoor play. All steps will be taken to prevent injury to your child and reduce risk. Water and first aid kits will be available. All personnel will also be First Aid /CPR certified. Furthermor e, both the YMCA and UTHSC personnel will be chaperoning all students. The UTHSC staff will follow the YMCA emergency procedures. UTHSC personnel will be present to oversee and evaluate educational and physical activity curriculum implementa tion, which will be conducted by YMCA staff.
	Questionnai re and	None	None	None	None	Estimated: Completion of the health questionnair e may make you feel uncomforta ble or cause troublesom e feelings or

	Surveys					emotions. You may refuse to answer any of the questions and you may take a break at any time during the study.
	Videotaping , Photograph y and Audio recording	None	None	None	None	Estimated: Having your photograph taken, your voice recorded, and being videotaped may make you feel uncomforta ble. You may take a break during any time of the study. There is also a potential risk of loss of confidentiali ty that someone who views your video and photograph er listens to your audio recording of the educational, physical activity, and evaluation sessions might identify you.
						Estimated: With wearing the activity monitors, if irritation of the skin occurs due to wearing the device,

	Activity Monitor	None	None	None	None	discontinue wearing the device and consult a doctor for treatment. Although the Polycarbona te and Polyvinyl Chloride materials are not known to be irritating to the skin, some irritation to people with sensitive skin may occur. If this happens, consult your doctor for treatment and stop wearing the device. Also, notify a research team member that gave you the activity monitor that you have taken the device off since data collection will be effected.
	Health Measures	None	None	None	None	Estimated: Possible risk of infection and bruising may occur with the finger stick procedure done to collect blood glucose and cholesterol levels, even if rare. Also, there is

					possible risk of being uncomforta ble while the health measures are performed.
--	--	--	--	--	--------------------------------------------------------------------------------

If some risks noted above require further discussion by the PI in order for the IRB to review this research, please discuss those risks here:

N	/A
	,

36.0 (2210) AE's and Data Monitoring

36.1 * Has an independent data and safety monitoring board (DSMB) been established for the conduct of the study/project?

- Yes. An independent data and safety monitoring board (DSMB) HAS been established for the conduct of the study/project.
- No. An independent data and safety monitoring board (DSMB) HAS NOT been established for the conduct of the study/project.
- * Please explain so that the IRB understands the data and safety monitoring arrangements that are in place for this research, or indicate that it is explained in the sponsor protocol:

The research team leverage the strengths of the collaboration between CFRI Biomedical Informatics Core (BMIC) and the Pediatric Obesity Program of the University of Tennessee Health Science Center (UTHSC) /Le Bonheur Children's Hospital (LBCH) to facilitate many aspects of statistical design, data storage, and analysis. Such strengths include infrastructure support from the UTHSC Information Technology Services (ITS) computer center and skilled personnel with expertise in diverse fields of clinical data management, clinical trials, registries, specific analytics, and well-resourced database technologies. The UTHSC network and computing facilities are owned and managed by UTHSC and all database instances are physically housed in the UTHSC ITS department computer center.

CFRI Biomedical Informatics Core (BMIC)

The Biomedical Informatics Core (BMIC) provides best-in-class informatics support to CFRI's operation and administration. This capability includes research information databases and web sites to provide information and foster communication among CFRI clinical and translational investigators. Vanderbilt University (VU), with collaboration from the Clinical & Translational Award (CTSA) consortium of institutional partners, has developed the Research Electronic Data Capture (REDCap™) for electronic collection and management of research and clinical trial data. The REDCap™ system provides secure, webbased applications that comprise intuitive interfaces for users to enter data. REDCap™ is flexible for various research areas. With planning assistance from BMIC informatics team, all members of the research team use a study-specific data dictionary, adaptive logic, and real time validation rules (features in REDCap™) which results in well-planned data collection strategy for individual research studies. Because REDCap™ is web- based, users with appropriate permissions can access the system from anywhere in the world with via an Internet connection.

REDCap[™] also provides a standard export mechanism to various types of common statistical packages (SPSS, SAS, Stata, R/S-Plus). This allows the Principal Investigator (PI) to generate data that are truly independent of the data entry method, thereby generating usable, collaborative datasets for outcome analysis. REDCap[™] was designed specifically to comply with HIPAA security and privacy guidelines. BMIC REDCap[™] servers are housed in a HIPAA-class server room with key card and passcode access protection. All web- based information transmission is encrypted and uses Secure Hypertext Transfer Protocol (HTTPS) employing SSL (Secure Sockets Layer) encryption technology. SSL creates the secure connection, and HTTPS transmits the data securely. REDCap[™] currently supports over 240 academic and non-profit consortium partners with over 26,000 research end-users (www.project-redcap.org).

UTHSC Information Technology Services (ITS)

UTHSC owns and manages its network and computing facilities. All REDCap™ instances are physically housed in the UTHSC ITS department computer center. This center has electric power conditioning, battery backup for short-term outages, and a backup diesel generator for long-term outages. The

computer center also has fire suppression, temperature and humidity control, card key controlled access and video monitoring. The UTHSC police force monitors the building which has after-hour access controls. Networking equipment across the campus is housed in dedicated and locked wiring closets with battery backups; access is limited to UTHSC network services personnel.

A 100-MB switched network with fully redundant network cores provides connections to both the Internet and Internet 2. Network traffic crossing the UTHSC network boundary is examined by a Cisco firewall against its Access Control Lists. A Cisco intrusion prevention system has been deployed to further examine traffic indicative of known exploits, and traffic is shunned or trapped as appropriate. Access from outside the UTHSC network for public data is to known web server ports and services. VPN (Virtual Private Network) access is available to authorized users by personalized NetID. No device may have network connectivity until its owner registers it; registration requires a University NetID and agreement with the UTHSC policy on acceptable use of computer resources. Systems at UTHSC are required to run current anti-virus software. All UTHSC systems are required to maintain current software patch levels.

Data security

The CFRI BMIC follows and implements all required information security standards. All deployed web applications use the standard industry practice of a dual server, consisting of a "front-end" web server accessible to the general Internet and a "back-end" database server accessible only to connections from the private network (and not from the public internet). All servers reside behind the UTHSC ITS unified threat management system, which is actively monitored. To provide greater data security and performance, the web server and database server are separated and do not reside on the same computer. To enable compliance with Good Clinical Practice (GCP) and regulatory guideline 21 CFR Part 11/45 CFR 164, user-controlled privileges are implemented in our central registry database.

To satisfy the NIST SP 800-44 requirement, the BMIC corporate information infrastructure includes an integrated firewall and intrusion detection system, backed up by continuous monitoring and automatic detection and alerts. The corporate network is divided into physical segments and logical zones. Network traffic crossing segments and zone boundaries is monitored and controlled. Access to and from the internet is limited to particular ports and firewall zones. Access to the host Web Server requires users to log in through Secure Hypertext Transfer Protocol (HTTPS) connections.

To maintain HIPAA compliance across our system, all Personal Identifiable Information (PII) and Limited Data Set are encrypted by FIPS 140-2 compliance encryption standard for the NIST. All communications use HTTPS, which employs state-of-the-art Transport Layer Security (TLS) protocol and SSL (Secure Sockets Layer) encryption technology. SSL creates the secure connection and HTTPS transmits the data securely.

Additionally, the CFRI BMIC recently participated in the Web Application Security Consortium (WASC) and Open Web Application Security Project (OWASP) community mailing list, wiki, and blog. The WASC and OWASP are 501(c)3 not-for-profit worldwide groups of experts focused on improving the security of application software and the best-practice security standards for the World Wide Web. Furthermore, CFRI's BMIC informatics architecture separates database and application functionality across servers. All servers are protected by UTHSC firewalls. Development/staging environments are separate from production environments. All coding design and implementation in REDCapTM are implemented through the development environment and source control. Security is considered in all phases of the system development life cycle and is treated as an integral part of the system development and implementation process, including system modifications. CFRI's BMIC development team leader ensures that adequate and effective management, operational and technical control mechanisms are integrated into the system development lifecycle.

Secure data access

REDCap™ has the ability to strictly control access to the data using role-based control. Granted access is based on the role of individual user. Examples include a general user or a privileged user such as an administrator, regular user, principal investigator, co-investigator, etc. Audit records include date and time of the event, subject identity, and success or failure of the event. The database can be queried through the web- based interface with an appropriate control access through Virtual Private Network (VPN) and login authentication. We will provide a unique assigned username and password, which will be required for authentication.

Our database (REDCap™) uses system authentication to connect to the application. The application enforces rights limitations and information flow control. Connectivity between application and database, and between users and applications, is limited by VPN, firewall filtering and service/application access control. Passwords for all user accounts expire every 90 days as part of our Standard Operating Procedures (SOPs). Users will be warned that their passwords are about to expire, beginning at least 14 days prior to the expiration date. User are notified via Rules of Behavior (RoB) that they must not share password with others and to report lost or compromised password immediately to the CFRI BMIC. The user session is dropped after 20 minutes of navigation inactivity. Because these applications are browser-based, user session is terminated. To continue, a user must log in to the application and establish a new session.

Data storage

Data are stored on a MySQL database server that is housed in UTHSC ITS HIPAA-class server room and protected by the UTHSC firewall. Access to the server room is protected by the use of key cards and personal security passcode access protection. The server uses a Redundant Array of Independent Disks

(RAIDs) configuration on the hard drives available in the event of a drive failure so drives can be replaced immediately. All data is moved to a backup server nightly. A tape backup is made of the two most recent full backups. These tapes are encrypted and stored in the server room before entering the rotation again. To militate data loss in the event of the disaster, CFRI's BMIC follows the UTHSC Disaster Recovery Plan (DRP) and Business Continuity Plan (BCP).

Vulnerability scan

The CFRI BMIC actively monitors for vulnerabilities in our security plan. This monitoring takes place at various levels of granularity. The top-level review is our internal Risk Assessment Retreat. This is quarterly meeting engages all developers, supervisors, and data managers as well as the systems, network, and database administrators to discuss perceived risks to our system. Attendees are invited to spend a number of hours preparing through the use of system reviews, log analysis, feasibility analysis, and white hat analysis. Internal CFRI BMIC policy dictates that a risk assessment be performed when configuration changes are made. This includes any creation or modifications of firewall rules, backup plan, database, roles, and internal user access. This ongoing review aims to identify possible problems or attacks on our servers early on. There could be unexpected utilization of the central processing unit (CPU), a large number of refused connections, or a drastic increase in web server traffic.

37.0 (2730) If Subjects Were Not to Participate

37.1 * List all of the procedures (including those such as medical record abstraction or survey administration) that will be performed ONLY because the subject is in this study/project. This means even listing how many additional blood draws, visits, etc., would occur beyond the number of standard of care blood draws, visits, etc. If all procedures are being performed solely for research purposes, you may simply state this.

All procedures are being performed solely for research purposes.

38.0 (2748) Privacy

- 38.1 * Confirm that ALL of the following are true:
 - the collection of private information will be limited to the minimum necessary to meet the objectives of the study; AND
 - the number of key study personnel (KSP) who have access to private information will be limited to the minimum number necessary to meet the objectives of the study; AND
 - research records will be kept separate from other records, such as medical or educational records, unless the information is useful for the welfare of the subject, or unless the clinic /hospital's policy is to include research consent forms in the patient's medical record.

ruited, and

	Yes, all of the above statements are true. No, one or more of the above statements are not true.	
